9.2 The STRIDE Intervention

Run-in Period. We will recruit up to 5 early-stage, hormone receptor-positive BCS who meet eligibility criteria to participate in the run-in period of the study, an approach to ensure smooth operation of study procedures.^{48,49} These participants will complete the entire intervention through the 3-month assessment (see Protocol Schema prior to Table of Contents). Participants will complete acceptability ratings of ease and usefulness (0-10 scale) at each session (Appendix 30.9). Participants will complete an additional STRIDE acceptability measure (including the CSQ) about their experience in the program as a whole after they complete the intervention (Appendix 30.18). At the 3-month assessment, we will conduct individual, semi-structured exit interviews to solicit feedback about the intervention, study procedures, and the assessment battery and ensure acceptability (Appendix 30.10).⁵⁰ Qualitative data will be recorded, transcribed, and thematically analyzed. Results will inform modifications such as refinement of the intervention, assessment battery, and study methods for feasibility testing in a pilot RCT. Any revisions made at that time to the intervention content or assessment battery will be re-submitted as amendments to the protocol and IRB approval will be obtained prior to beginning of the RCT.

STRIDE Intervention. The intervention content is included in Appendix 30.11. STRIDE is a brief, group-based, videoconference intervention with six weekly one-hour sessions and two follow-up 15-30-minute phone check-ins at month four and five. The STRIDE intervention incorporates aspects of *CBT for Adherence and Depression*,⁴¹ employing symptom management, cognitive restructuring, behavioral activation, and skills-based methods to address adherence and psychiatric symptoms. The first three sessions entail an assessment of patient, treatment, and healthcare system/provider barriers to adherence, followed by psychoeducation about breast cancer risk and benefits and risks of AET. We will employ specific interventions to target patient-identified barriers. For example, cognitive reframes will be applied to optimize accuracy related to recurrence risk perception and clinical necessity for therapy. Problem-solving will be implemented for management of financial distress (e.g., develop plan with social work and oncology team). To target healthcare system/provider barriers, the protocol will teach assertiveness skills for adopting an active role with clinicians and increasing self-efficacy. The last three tailored sessions will target treatment factors; patients will receive training in symptom management and coping strategies specific to the side effects or symptoms that they endorse. CBT is effective in helping patients manage cancer-related side effects such as pain, fatigue, and menopausal symptoms such as hot flashes. CBT strategies will address individual sources of distress, such as difficulty managing symptoms, or financial concerns around medication cost that are interfering with adherence and exacerbating distress. In extenuating circumstances, participants may be scheduled for individual sessions if we cannot schedule them for a group session within a reasonable amount of time.

Participants in the STRIDE intervention will continue to monitor medication-taking with the MEMS Caps throughout the 24-week study period. As part of the intervention, participants will practice relaxation training using study recordings through the study's website portal

(stridestudy.mgh.harvard.edu). The structure of each website post can be viewed in Appendix 30.25. The website will move into production after IRB approval. This is a website created with the support of IT at MGH/HMS and is viewable to those with the link to the website URL. The website will contain no advertisements or other content. It will only contain the relaxation file, and the individual sessions from the work book that the intervention participants receive, so that they can also have an electronic version accessible for the future. Study staff will provide instructions for participants to access this website via email as part of the intervention session reminders (Appendix 30.14). In addition to the overall study PI, [name], trained clinical psychology practicum students, clinical psychology fellows, licensed psychologists or social workers on the study team at MGH will deliver the intervention, to ensure successful administration of the intervention. Interventionists will complete a post-intervention survey for each group intervention, which will document process variables such as session length, session interventionist, and session attendance. [name] has ample experience delivering this type of intervention and was a protocol therapist on several NIH-funded CBT-based studies. She will conduct weekly clinical supervision with trained interventionists. 80% of sessions will be audio-recorded and at least 10% randomly selected, stratified by interventionist, and reviewed with [name] for treatment fidelity. Content fidelity will be assessed by calculating the percentage of key intervention topics addressed out of total topics, with a goal of 90%.⁵¹ Feedback will be given to interventionists to enhance adherence to the protocol.

Finally, participants who identify as part of a racial/ethnic minority population will be offered the opportunity to participate in a qualitative exit interview to provide feedback on the STRIDE program.

Medication Monitoring Control. Participants in the comparison condition will not receive the STRIDE intervention; however, they will monitor medication-taking with MEMS Caps and undergo standard care with oncology follow-up.

Rationale: Although we considered an attention-matched condition to control for nonspecific intervention effects, we decided against this approach because medication monitoring is likely to improve adherence alone.⁵² Additionally, requesting participation in a placebo intervention adds undue burden to BCS who are coping with emotional and physical sequelae. Finally, an attention control should only be employed if attention would affect the primary outcome. Since no data suggest that attention would improve AET adherence, an attention control would be an added expense and unethical.⁵² Finally, participants who identify as part of a racial/ethnic minority population will be offered the opportunity to participate in a qualitative exit interview to provide feedback on the STRIDE study.

Retention. Strategies to promote retention will include accurate explanations of study expectations during the recruitment process,⁵³ collection of locator information and a secondary contact (Appendix 3.12), a phone check-in to ensure use of MEMS Caps, branding of study materials for project identity, and reimbursement for time (\$20/assessment). Intervention participants will receive a text reminder one day prior to the scheduled ZOOM session (See Section 5.2 detailing Participant Communication).

9.3 *Study Instruments*

The following questionnaires have been specifically selected to reflect the theoretical intervention targets and aims of the study. All participants will complete the baseline questionnaires within four weeks of documented informed consent. If a participant does not complete the baseline questionnaires within this timeframe, she will be re-screened and re-consented, restarting the four-week window. Follow-up assessments will be completed at 12-week (+/- 2 weeks) and 24-week (+/- 2 weeks) from time of baseline completion (Appendix 30.16) Table 3 details the schedule for administering all study instruments. Patient assessments can be found in Appendix 30.16. We anticipate that 15-20% of 12-week assessments will be out

of window for intervention participants, given the occasional delay of coordinating multiple patients' schedules to arrange the intervention groups.

Instrument/Measure:	Screening	Baseline (4-week window from consent)	12-weeks post-baseline (+/- 2-week window)	*24-weeks post-baseline (+/- 2-week window)
Chart review	X			
Adapted NCCN Distress Thermometer	X			
Medication Event Monitoring System (MEMS Caps)		To be used throughout the 24-week study period		
Demographics		X		
Medication Adherence Report Scale (MARS-5)		X	X	X
Breast Cancer Prevention Trial Symptom Checklist (BCPT)		X	X	X
Cancer Therapy Satisfaction Questionnaire (CTSQ)		X	X	X
Hospital Anxiety and Depression Scale (HADS)		X	X	X
Functional Assessment of Cancer Therapy (FACT-B)		X	X	X
Measure of Current Status (MOCS)		X	X	X
Beliefs About Medications Questionnaire – Adjuvant Endocrine Therapy (BMQ-AET)		X	X	X
Multidimensional Scale of Perceived Social Support (MSPSS)		X	X	X
Self-Efficacy in Appropriate Medication Use Scale (SEAMS)		X	X	X
Self-Efficacy For Managing Symptoms and Taking AET Questionnaire (Self-Efficacy For Symptoms)		X	X	X
Patient-Reported Outcomes Measurement Information System (PROMIS) – Cognitive Function – Short Form 4a		X	X	X
Client Satisfaction Questionnaire (CSQ)**			X	
Supplemental Medication Diary	To serve as optional as-needed supplement to MEMS Caps (e.g., on vacation)			
Session Rating Form	To be administered during the run-in period after each intervention session			
Intervention Acceptability Form	To be administered during the run-in period at 3-months post-baseline			
Semi-structured Exit Interview	To be conducted during the run-in period at 3-months post-baseline			
Semi-structured Exit Interview	To be conducting during the RCT period after participants complete their participation in the STRIDE program.			

*Run-in participants will not complete a 24-week assessment

**CSQ will be administered to intervention participants only

Screening:

Adapted National Comprehensive Cancer Network (NCCN) Distress Thermometer (Included as part of Study Screening Script in Appendix 30.3 and independently in Appendix 30.17): The NCCN Distress Thermometer is a valid, one-item measure for assessing distress in many cancer populations.⁵⁴ This

measure is scored on a range of 0 (no distress at all) to 10 (extremely distressed), and a score of 4 has been identified as an appropriate cut-off to measure significant distress.⁵⁵ This measure has been modified in this study for the purpose of screening BCS for distress related to taking AET, distress related to breast cancer symptoms/side effects, and distress related to adherence to AET. Participants who indicate a score of ≥ 4 on any of the three distress thermometers will be eligible for participation.

Secondary Outcomes:

Medication Event Monitoring System (MEMS Caps):¹³ MEMS Caps will be used to electronically monitor AET daily dose and timing of dose administration. MEMS Caps are widely used in adherence monitoring including for patients with breast cancer.^{34,56,57} Prescribed medication, dose, and timing will be identified in the Electronic Health Record and verified by the patient. Adherence will be calculated as the percentage of medication taken of the total prescribed. A total monthly and weekly adherence score will be calculated to examine changes over time.

Supplemental Medication Diary (Appendix 30.23): The Supplemental Medication Diary will be used per participant discretion alongside their use of the MEMS Caps. The diary will allow participants to document any instance in which they take their AET without opening the MEMS Cap. For example, a participant would document use in the diary if they took out two doses to be taken for the next two days, without opening their MEMS again.

Medication Adherence Report Scale (MARS-5): The MARS-5 assesses adherence to treatment and has been used specifically in the context of AET adherence. The scale consists of five items that ask about suboptimal adherence behaviors, such as “I stop taking my adjuvant endocrine therapy medicine for a while.” Each item is answered on a scale of 1 (Always) to 5 (Never).⁵⁸

Cancer Therapy Satisfaction Questionnaire (CTSQ): The Cancer Therapy Satisfaction Questionnaire (CTSQ) is a previously published 21-item measure that evaluates patients’ beliefs about the following aspects of medical care: expectations of the effectiveness of cancer therapy, feelings about side effects, oral cancer therapy adherence, satisfaction with cancer therapy, stopping cancer therapy, and reasons for non-adherence.⁵⁹

Breast Cancer Prevention Trial Symptom Scale (BCPT): The BCPT is a symptom checklist used to document physical and psychological symptoms associated with ET use.⁶⁰ The measure includes several clinically-relevant symptom subscales and has been used broadly in previous studies on symptom distress in breast cancer patients. The BCPT asks participants to rate how much they have been bothered by several symptoms over the past week on a scale of 0 (Not at all bothered) to 4 (Extremely bothered).

Exploratory Outcomes:

Hospital Anxiety and Depression Scale (HADS):⁶¹ The HADS is a valid self-report measure for assessing anxiety and depressive symptoms among patients in non-psychiatric hospitals.⁶² The 14-item measure contains seven questions to assess depressive symptoms and seven questions to assess anxiety symptoms to distinguish between the two. Patients indicate how they have been feeling on average over the past week. Each item is answered on a scale of 1 to 4. The four possible answer choices vary and adjust for each question.

Functional Assessment of Cancer Therapy-Breast Cancer (FACT-B): The FACT-B is a validated measure used to assess multidimensional quality of life in patients with breast cancer. The measure captures five domains: physical well-being, social/family well-being, emotional well-being, functional

well-being, and additional concerns. Each item is answered on a scale of 0 (not at all) to 5 (very much).⁶³

Self-Efficacy for Appropriate Medication Use Scale (SEAMS):⁶⁴ The SEAMS will be used to measure patient self-efficacy in taking medication. The SEAMS was developed specifically for patients with chronic disease taking long-term medication.⁶⁴ Two factor structures are created: self-efficacy for taking medication under difficult circumstances and under changing circumstances. Each item is answered on a scale of 1 (not confident) to 3 (very confident).

Covariates:

EHR Factors: The following information will be collected from participant EHR: MGH Main vs. Affiliate site, health insurance type, breast cancer stage, treatment (e.g., surgery, chemotherapy, radiation), ET type, time since treatment completion, menopausal status, psychotropic medications, and medical or psychological co-morbidities.

Demographic Questionnaire: Participants will self-report their age, gender, race/ethnicity, marital status, education level, and relationship status.

Multidimensional Scale of Perceived Social Support (MSPSS):⁶⁵ The MSPSS is a validated, reliable scale used to capture levels of perceived social support. The scale consists of 12 items, such as “my family really tries to help me,” and is measured on a 7-point Likert scale.

Potential Mediators

Beliefs about Medicines Questionnaire – Adjuvant Endocrine Therapy (BMQ-AET):⁶⁶ The BMQ-AET will be administered to assess beliefs about the need for AET. The BMQ-AET has been used in studies measuring endocrine therapy adherence.⁶⁷ This study will use one of the two scales, which is computed measuring perceived need for medication and concerns about disruptive medication effects.

Measure of Current Status (MOCS): The MOCS is a 13-item scale which measures patients’ current self-perceived ability on several skills. Examples of targeted content areas are ability to relax, restructure maladaptive thoughts, and choose appropriate coping responses. Each of the 13 items is answered on a scale of 0 (I cannot do this at all) to 4 (I can do this extremely well).

Self-Efficacy For Managing Symptoms Questionnaire (Self-Efficacy For Symptoms):⁶⁸ The Self-Efficacy for Symptoms Questionnaire is a modified version of the self-efficacy scale to assess patient self-efficacy in managing symptoms related to their endocrine therapy medication. The measure asks patients to rate their confidence on a scale of 1 (not at all confident) to 10 (very confident) in their ability to decrease or control the side effects of their medication.

Potential Moderator

Patient-Reported Outcomes Measurement Information System (PROMIS) – Cognitive Function – Short Form 4a:⁶⁹ The PROMIS short-form measure will be used to assess patient-perceived changes in cognitive function.⁷⁰ The 4-item measure asks patients to response to each statement on a scale from 1 (very often) to 5 (never) over the past 7 days.

Intervention Acceptability:

Client Satisfaction Questionnaire (CSQ):⁷¹ The CSQ is a 3-item, validated measure to assess satisfaction with services provided to the patient, and asks questions such as, “to what extent has our program met

your needs?” Each item is answered on a scale of 1-4. This will be administered at the 12-week assessment to evaluate intervention participants only to examine intervention acceptability.

Run-in participants only:

Session Rating Form (Appendix 30.9): This 5-item measure will be given to run-in participants to capture their thoughts and perceptions of the usefulness of each STRIDE intervention session. An example of a question is, “how enjoyable was today’s session?” Each question will be answered on a scale of 1-10.

Intervention Acceptability Measure (30.17): This measure will be given to run-in participants only at the 10-week post-baseline question. The goal of this measure is to capture participant thoughts and experiences having gone through the STRIDE Intervention. An example of an item is “how satisfied are you with the number of sessions (5) that you received?” and is to be answered on a scale of 1 (quite dissatisfied) to 4 (very satisfied).

Semi-Structured Interview (Appendix 30.10): At the end of the run-in period, participants will complete a brief semi-structured interview to assess the STRIDE Intervention. This interview will be conducted with a study staff member not involved with the delivery of the intervention and will be used to inform and adapt the STRIDE Intervention for the RCT.

Semi-Structured Interview (Appendix 30.11): At the end of the RCT period, participants who identify as part of a racial/ethnic minority population will complete a brief semi-structured interview to assess the STRIDE Intervention. This interview will be conducted with a study staff member not involved with the delivery of the intervention and will be used to inform and adapt the STRIDE Intervention for the next phase of the study to increase its cultural awareness and relevance.

9.4 Data Collection

Participants will be given the option to complete the above instruments either on paper or over a secure REDCap portal. Study staff will send assessments to participants at the start of their timepoint window and will follow-up periodically throughout to ensure receipt and completion of assessments. Assessments that are completed on paper will be entered into the secure REDCap database by study staff.

Patients assigned to the intervention arm will additionally receive a copy of the Intervention Manual, a welcome letter with study expectations (Appendix 30.11), and a study timeline document (Appendix 30.15) to better their understanding of what time points to expect throughout the study.

Patients randomized to the usual care arm will follow standard care of Massachusetts General Hospital Cancer Center. They will also receive a study timeline document (Appendix 30.15).

10.0 Data and Specimen Banking: Not applicable

11.0 Data Management* and Confidentiality

11.1 Data Analysis

To determine feasibility in a pilot randomized controlled trial (N=100), estimate effect size, and finalize the intervention and study protocol to plan a full-scale, adequately powered efficacy trial.

Power calculation. The primary objective of this pilot study is to demonstrate feasibility, defined as (1) enrollment rate > 50%, (2) retention rate > 70%, and (3) attendance rate \geq 70% (i.e. \geq 70% of participants complete at least 4 of 6 sessions). At the time of the original protocol approval, we

estimated an accrual goal of 80 (75 in RCT and 5 in run-in phase) participants; therefore, the following power estimates are based on that number. We estimated that the enrollment rate will be 60%. If 134 patients are approached and 80 are enrolled, the lower limit for an exact, one-sided 95% confidence interval for the estimated enrollment rate will be 53%. Furthermore, we anticipate that the retention and attendance rates will both be 80%, and with 80 enrolled participants, the lower limit for an exact, one-sided 95% confidence interval for the retention and attendance rates will be 71%. Thus, based on our estimates of the feasibility parameters, the study will demonstrate feasibility of the adherence intervention. We have now expanded our accrual goal to 100 participants, which serves to only increase our power and rates of enrollment, retention, and attendance.

Primary Aim. To examine the feasibility and acceptability of a tailored, small-group, Telehealth intervention (STRIDE) compared to a medication monitoring control for survivors of breast cancer taking adjuvant endocrine therapy.

Hypothesis 1: The study will be feasible, defined by recruitment (enrollment rate > 50%), retention (completion rate of follow-up assessments > 70% of all participants who complete baseline) and attendance (attendance rate of at least 70% of participants completing at least 4 of 6 sessions [60%]).

Hypothesis 2: The study will be acceptable demonstrated by >75% of participants reporting average satisfaction scores greater than the scale's mid-point (Client Satisfaction Questionnaire).

Secondary Aim. To assess effects of the STRIDE intervention on adherence to AET, symptom distress, and satisfaction with AET.

Hypothesis 1. We hypothesize that participation in the STRIDE intervention will be associated with an increase in adherence and satisfaction with AET and a decrease in symptom distress at 12-weeks compared to the medication monitoring control, and that these improvements will maintain at 24-week follow-up.

Data will be assessed for patterns of missingness⁷² and statistical assumptions. We will conduct mixed effects models with repeated measures data and relevant covariates such social support (MSPSS) and demographic and treatment-related factors (e.g., age, stage, time since AET initiation) as potential covariates. Longitudinal analyses will include all time points and a cross-sectional analysis for each time point. Given that this pilot is not powered to detect statistically significant group differences, we will examine mean differences and sample variability. Effect sizes (Cohen's d) will be calculated for changes in outcomes from baseline to four and eight months, as (Mean change score [intervention arm] – Mean change score [control arm])/SD pooled, where 0.3 indicates a small effect, 0.5 a medium effect, and 0.8 a large effect.⁷³ Effect sizes will be used in a power analysis to estimate the necessary sample size to conduct a full-scale efficacy trial with power >80%. We will also verify the needed sample size based on ability to detect a clinically meaningful difference and references to existing literature.⁷⁴

Exploratory Aim. To assess the effects of the STRIDE intervention on several psychosocial constructs, exploring potential mediator and moderators of the intervention.

Exploratory Hypothesis: We will explore whether participation in the STRIDE intervention is associated with an increase in QOL and medication-taking self-efficacy, and a decrease in distress (anxiety and depression at 12-weeks compared to the medication monitoring control, and whether these improvements are maintained at 24-week follow-up.

We will use the same procedure to assess changes in secondary outcomes in the intervention group. We will explore potential mediation of secondary and exploratory endpoints through changes in beliefs about adjuvant endocrine therapy (BMQ-AET) and/or perceived coping skills (MOCS), as well as self-efficacy for managing symptoms (Self-Efficacy For Symptoms).

Potential demographic or treatment related moderators will also be explored (e.g., age, type of AET medication, cognitive functioning [PROMIS]). We will conduct moderated regressions to examine whether a group difference in adherence is moderated by age, social support (MSPSS), employment status, menopausal status, medication type, or other patient/treatment factors. We will explore alternative models using dichotomous outcomes over time.

Findings will inform the planning of an R01 to evaluate the efficacy of a videoconference, tailored intervention in improving ET adherence for BCS. If the current study is not found to be feasible or acceptable, we will have acquired valuable information to proceed in the identification of a patient-centered intervention for BCS. For example, feedback from the final assessment can be used to modify the intervention, such as the addition of a systems-based intervention component if findings show that low health literacy or cost barriers influence intervention effects. Differences in adherence, feasibility, or acceptability based on demographic or clinical characteristics can help determine which individuals may benefit. Ultimately, this project will contribute to the understanding of BCS' needs related to ET. Future studies based on these findings have the potential to influence survivorship care plans, and videoconferencing is a modality that can be widely disseminated. Improved adherence to ET may prevent recurrence and mortality, extending the lives of BCS.

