This will be the first study to develop and test an evidence-based intervention that is flexible, portable, and tailored to address AET adherence barriers unique to BCS. The proposed strategy implements a mixed-methods design based on the ORBIT model,¹ integrates a comprehensive conceptual framework, adapts an established, evidence-based treatment, and employs novel technologies in the following three ways: 1) Tailored intervention content. 2) Videoconferencing. The use of tele-mental health ZOOM technology limits barriers to treatment such as cost, time, and travel, thereby increasing access to behavioral health interventions.⁸ We will extend the use of videoconferencing to BCS reporting difficulty managing their AET. 3) Objective, electronic measurement. Since self-report methods tend to yield overestimates of adherence,⁹⁻¹² We will use the Medication Event Monitoring System (MEMS¹³) in addition to self-report measures. Thus, this study employs existing technologies in a novel setting to model longitudinal change in AET adherence in the intervention and control groups.¹³

Specific Aims

1. **Primary Aim.** To examine the feasibility and acceptability of a tailored, small-group, Telehealth intervention (STRIDE) compared to a medication monitoring control for survivors of breast cancer taking AET.

Hypothesis 1: The study will be feasible, defined by recruitment (enrollment rate > 50%), retention (follow-up assessment completion rate > 70% of all participants who complete baseline) and attendance (attendance rate of at least 70% of participants completing at least 4 of 6 sessions [67%]).

Hypothesis 2: The study will be acceptable demonstrated by >75% of participants reporting average satisfaction scores greater than the scale's mid-point (Client Satisfaction Questionnaire).

2. **Secondary Aim:** To assess effects of the STRIDE intervention on adherence to AET, symptom distress, and satisfaction with AET.

Hypothesis 2: We hypothesize that participation in the STRIDE intervention will be associated with an increase in adherence and satisfaction with AET and a decrease in symptom distress at 12-weeks compared to the medication monitoring control, and that these improvements will maintain at 24-week follow-up.

3. **Exploratory Aims:**

- a. To assess the effects of the STRIDE intervention on several psychosocial constructs, exploring potential mediator and moderators of the intervention.

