8.0 Study Endpoints*

8.1 Primary Endpoint:

The primary endpoint is feasibility and acceptability as measured by participant rates of enrollment (>50%), participant retention (>70%), intervention attendance (>70% attending at least 4 of 6 sessions), and intervention satisfaction (>75% reporting average satisfaction greater than the scale's midpoint).

8.2 Secondary Endpoints:

The secondary endpoints of the study are as follows:

- Changes in adherence between groups on objective MEMS Caps and self-report MARS-5* at 12-weeks and 24-weeks post-baseline (changes in MEMS Caps adherence will be compared across the entire 24-week period).
- Changes in self-reported satisfaction with AET on the CTSQ* between groups at 12-week and 24-weeks post-baseline.
- Changes in self-reported symptom distress on the BCPT* between groups at 12-week and 24-weeks post-baseline.

Secondary endpoints will also be examined using social support (MSPSS*) and demographic and treatment-related factors (e.g., age, stage, time since AET initiation) as potential covariates.

8.3 Exploratory Endpoints:

- Changes in distress levels (HADS*), quality of life (FACT-B*), and medication self-efficacy (SEAMS*) between groups at 10- and 24-weeks post-baseline, as well as potential mediation of secondary and exploratory endpoints through changes in beliefs about adjuvant endocrine therapy (BMQ-AET*), self-efficacy for managing AET symptoms (Self-Efficacy For Symptoms) and/or perceived coping skills (MOCS*). Potential demographic or treatment related moderators will also be explored (e.g., age, type of AET medication, cognitive functioning [PROMIS*]).

*All study instruments are explained in full in Section 9.3.

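### The 71% lower limit for attendance counts control participants, who have no sessions; on the STRIDE arm alone it is about 68% (40 of 50, assuming 1:1 allocation), below the 70% threshold

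*Combined protocol and SAP*

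**What the plan says.** The power calculation in Section 11.1 rests on the original accrual of 80, made up of 75 randomised and 5 run-in participants. It states that "we anticipate that the retention and attendance rates will both be 80" percent, and then that "with 80 enrolled participants, the lower limit for an exact, one-sided 95% confidence interval for the retention and attendance rates will be 71" percent. From these limits it concludes that "based on our estimates of the feasibility parameters, the study will demonstrate feasibility of the adherence intervention". It then notes the expansion to 100, "which serves to only increase our power and rates of enrollment, retention, and attendance", without recalculating any limit.

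Attendance is one component of the primary endpoint. Hypothesis 1 under the Specific Aims asks for an "attendance rate of at least 70% of participants completing at least 4 of 6 sessions". Section 8.1 words it as "intervention attendance (>70% attending at least 4 of 6 sessions".

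Section 9.2 settles who has sessions to attend. For the control arm: "Participants in the comparison condition will not receive the STRIDE intervention". For the run-in group: "These participants will complete the entire intervention through the 3-month assessment".

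**The concern.** Retention and attendance do not share a denominator. Retention is counted over both arms. Attendance can be counted only in people who were offered sessions, so the controls drop out and the sample falls to roughly half. A lower limit that clears 70% by about one point with 80 people is unlikely to survive that.

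This is the only precision figure the plan gives for attendance, and the paragraph uses it to argue that the feasibility threshold will be cleared. A reader planning the full-scale trial would credit the pilot with more precision on attendance than its design provides. The closing remark about expansion adds to this: a larger sample narrows the interval but does not raise the underlying rates.

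**Working it through.** **Inputs**

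- Anticipated attendance 80%; exact one-sided 95% limit; N = 80 as 75 + 5 (Section 11.1).
- Threshold 70% (Specific Aims, Sections 8.1 and 11.1).
- Controls have no sessions (Section 9.2).
- Current randomised total 100 (Sections 4.0 and 7.0).
- Allocation ratio: not stated in words, so 1:1 is assumed. The readable rows of the randomisation list in Appendix 30.8 show 12 Arm B and 13 Arm C in the elevated stratum, and 6 and 6 in the not-elevated stratum. That is 18 intervention to 19 control.

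**Formula**

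For x attenders out of n, the exact (Clopper-Pearson) one-sided 95% lower limit is the 5% quantile of a Beta(x, n − x + 1) distribution.

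**Step 1: reproduce the plan's figure.** 80% of 80 is 64, and 64/80 gives 71.2%. This matches the stated 71%. The two-sided version gives 69.6% and does not match, so the stated figure is the one-sided limit on all 80.

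**Step 2: retention.** Retention covers both arms, so 71% is a fair figure. With the 75 randomised participants only, 60/75 gives 70.9%, which also rounds to 71%.

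**Step 3: attendance on STRIDE participants.** Where 80% of n is not a whole number, the nearest count is used.

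| Basis | n | x | Rate | Lower limit |
|---|---|---|---|---|
| Original, half of 75 | 37 | 30 | 81.1% | 67.4% |
| Original, half of 75 | 38 | 30 | 78.9% | 65.2% |
| Original plus 5 run-in | 42 | 34 | 81.0% | 68.3% |
| Original plus 5 run-in | 43 | 34 | 79.1% | 66.3% |
| Current, half of 100 | 50 | 40 | 80.0% | 68.4% |
| Current plus 5 run-in | 55 | 44 | 80.0% | 69.1% |

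Every row is below 70%.

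**Step 4: sensitivity to allocation.** With 40 to 60 of the 100 randomised participants in the STRIDE arm, the limit runs from 66.8% (32/40) to 69.6% (48/60). Checking n in steps of five at exactly 80%, the limit first passes 70% at n = 65 (52/65 gives 70.1%).

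**Step 5: what 50 STRIDE participants can show.** A lower limit above 70% needs at least 41/50 (82%), which gives 70.7%. If true attendance is 80%, the binomial chance of 41 or more out of 50 is 44%.

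**Step 6: the criterion as worded.** With n = 50 and true attendance 80%, the chance that the observed rate is at least 70% (35 or more) is 97%. The chance that it is above 70% (36 or more) is 94%.

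**The case against.** The strongest reply is that no section makes a confidence limit the rule for success. The Specific Aims, Section 8.1 and Section 11.1 all set the threshold on the rate, and with 50 participants and 80% true attendance it would be met 94% to 97% of the time. At 40/50 the limit falls short by only 1.6 points, and one more attender clears it. This stands, and it bounds the importance of the point. It does not rescue the paragraph, which argues from the limits and gives a figure for attendance that the design cannot produce.

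The paragraph also says openly that its figures use the original accrual. That is true, but the original STRIDE arm was smaller than the current one, so the gap on that basis is wider.

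The rows with run-in participants are open to challenge. The preliminary studies text in Section 2.0 says the intervention became six sessions after the run-in. The session rating form (Appendix 30.9) lists five sessions, and the acceptability measure (Appendix 30.19) refers to five. A criterion of 4 out of 6 may therefore not fit those participants. Those rows are only a sensitivity check, and without them the attendance limits are no higher.

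Finally, 60 STRIDE participants plus 5 run-in would reach 70.1%. A 60:40 split does not fit the 18 to 19 seen in the randomisation list.

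**Conclusion.** The concern holds. The 71% is calculated correctly for 80 people, but 80 is the wrong denominator for attendance. On the STRIDE arm, at close to 80% attendance, the exact one-sided 95% lower limit is 65% to 67% under the original accrual (30/38 and 30/37) and 68.4% under the current one (40/50). The inference that attendance clears 70% at its lower limit fails on the plan's own rate and method.

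The result rests on 1:1 allocation, which is not stated but is supported by the randomisation list; 40 to 60 STRIDE participants out of 100 gives the same conclusion. The error is confined to the stated precision and the sentence built on it. The sample size, the endpoint definition and the 71% for retention are unaffected. It should be fixed, as a correction to the planning text.

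**What to change.** Revise the power calculation in Section 11.1 as follows.

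- Keep 71% for retention only, and label it as based on the original accrual of 80. If the paragraph is moved to the current accrual, 80/100 gives 72.3%.
- For attendance, state that with 50 STRIDE participants and 80% attendance the lower limit is 68%, and that at least 41/50 (82%) is needed for a lower limit above 70%.
- Limit the sentence concluding that feasibility will be demonstrated, so that it no longer relies on an attendance limit above 70%. Say that success is judged on the observed rate. Settle whether the threshold is at least 70% (Specific Aims, Section 11.1) or above 70% (Section 8.1); with 50 participants the two differ at 35/50.
- Replace the statement that expansion increases the rates with one that it increases precision.
- State the allocation ratio.

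The cost is a wording change in one paragraph, plus alignment of the threshold wording. No extra patients are needed, and the analysis does not change. The drawback is that the stated attendance precision becomes less favourable, at 68% instead of 71%.
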